#### 9.2 SAMPLE SIZE DETERMINATION

The estimated duration of this protocol is 36 months and we anticipate recruiting 1-2 subjects a month over this period.

The primary outcome measure is the MADRS total score. The null hypothesis is that the 95% confidence interval for the effect of drug (TS-161 minus placebo) on MADRS total at 3 weeks, after controlling for baseline scores, will include zero; the alternative hypothesis is that this 95% CI will be less than and exclude zero. We have observed in previous crossover studies of the rapid acting antidepressant ketamine an estimated difference of -6.7 (SE = 1.5) [95%CI: -9.6, -3.76]. This study will be powered to detect an effect within that confidence interval that translates to moderate effect size (difference = -7.5; d = 0.70) on the MADRS total score at end point. While we are primarily interested in identifying drugs with a large effect size, this effect size was selected to balance the risk of an underpowered study if the true effect size were not large and the cost of powering the study to detect a small effect size. Assuming  $\alpha$ =.05, two-tailed, 20 patients with MDD would provide 80% power to detect a drug effect of this magnitude at end point. As discussed, we are interested only in a moderate effect size and have powered the study accordingly. However, if we were to power the study based on the reasonable range of treatment effect observed in the previous studies of rapid acting antidepressants, the sample size requirements would range from 13 subjects for the largest effect in the 95% CI to 67 subjects for the smallest effect. To account for a 25% rate of attrition, either from participants who do not complete the drug-free period or who drop out during the crossover double-blind portion of the study, we will recruit 25 participants. No interim analyses are planned. Secondary analyses with continuous outcomes will likely be sufficiently powered, as we anticipate that the effects on most secondary outcomes will be similar to the primary outcome. However, the power of the study to detect effects on the categorical secondary outcomes (response and remission) will be reduced as categorical outcomes de facto require a larger sample size. SAS 9.4 PROC POWER for paired mean designs was used for sample size calculations.

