## 9.4.2 Analysis of the Primary Endpoints

The primary aim will be accomplished by assessing the efficacy of three weeks of oral TS-161 (50 to 100 mg/day) compared with placebo in improving overall depressive symptomatology. The primary assessment of efficacy is a comparison of MADRS scores between treatment groups. The MADRS total score is measured at the interval level, and although repeated measurement of the outcome is obtained the primary hypothesis concerns the value at 3 weeks.

The difference between TS-161 and placebo will be examined using a mixed model for repeated measures with restricted maximum likelihood estimation where drug and time are within subjects factors. Fixed effects for drug, time period, and their interaction will be specified. Period-specific baseline scores and the subject-specific average baseline score will be entered as a covariate (Kenward and Roger 2010); no other covariates will be included *a priori*. The degrees of freedom will be corrected using the Kenward-Roger approach. The residual covariance matrix will account for nesting of observations within period for each participant; during the model fitting stage, fit indices (e.g., Schwarz's Bayesian criteria) will be used to determine the most appropriate structure for the residual covariance matrix, including the possibility that it will be specified by drug to allow for heteroscedasticity. Also, during the model fitting stage, a subject-specific (random) intercept will be tested and retained if indicated by model fit indices. During the model

fitting stage, the residuals will be graphically assessed for distribution and spread; if they violate the assumptions of the model then appropriate transformations will be applied before selecting the final model. The analysis will be performed in the ITT sample, and missing data may occur. Maximum likelihood estimation will be implemented, which allows for missingness without excluding the participant; no imputation will be performed. The effect of interest in this model is the effect of drug at the 3-week timepoint (with 95% CI), which will be obtained from the drugby-time interaction using a contrast statement. Cohen's d, calculated using the model-estimated difference between groups, the standard error of that difference, and the degrees of freedom associated with that comparison, will be used to describe the effect size.

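### The term that pairs a patient's two periods is kept only if fit indices favour it, and no other between-period covariance is fixed, so the primary analysis may lose the pairing assumed in the sample size

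*Combined protocol and SAP*

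**What the plan says.** Section 9.4.2 specifies a mixed model for repeated measures in which drug and time are within-subject factors, with period-specific and subject-average baseline scores as covariates. Three of its statements bear on how a patient's two periods are linked:

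- On the subject effect: "a subject-specific (random) intercept will be tested and retained if indicated by model fit indices".
- On the residual matrix: "The residual covariance matrix will account for nesting of observations within period for each participant".
- On choosing that matrix: "fit indices (e.g., Schwarz's Bayesian criteria) will be used to determine the most appropriate structure for the residual covariance matrix".

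The section gives no list of candidate structures. It does not say that a between-period covariance stays in the model whatever the fit.

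Section 9.2 sizes the trial on the opposite premise: "SAS 9.4 PROC POWER for paired mean designs was used for sample size calculations". It states that, "two-tailed, 20 patients with MDD would provide 80% power to detect a drug effect of this magnitude at end point", where the magnitude is a "moderate effect size (difference = -7.5; d = 0.70) on the MADRS total score at end point".

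Section 9.4.3 applies the primary model to the other rating scales, and a similar model with a binary logistic outcome and no baseline covariate to response and remission.

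**The concern.** In a two-period crossover the pairing is a fact of the design. The drug contrast is taken within patient, and its variance is smaller than that of a two-group comparison by the factor 1 − ρ, where ρ is the between-period correlation. Whether the model respects this should not depend on a selection step with about 20 patients, where a fit index has little information about ρ.

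If the residual matrix is blocked by period and the intercept is dropped, the model holds no random link between a patient's two periods. The standard error of the week-3 contrast is then computed as if two separate groups had been compared. The confidence interval is too wide when ρ is positive. Cohen's d also shifts, because Section 9.4.2 derives it from that standard error and its degrees of freedom. The analysis no longer matches the paired calculation that justified 20 completers.

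**Working it through.** **Inputs.** From Section 9.2: two-sided alpha 0.05, 20 completers, difference −7.5, d = 0.70. Reading d as the mean difference over the SD of the paired difference, that SD is 7.5/0.70 = 10.71. The documents give no between-period correlation, so ρ is an assumption, taken from 0.2 to 0.6.

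**Step 1: the plan's own figure.** For a paired t-test with n pairs, the noncentrality is d√n on n − 1 degrees of freedom. With n = 20 it is 0.70 × √20 = 3.13, and power is 84.4%. With n = 19 power is 82.3%, so 19 is the smallest n that reaches 80%. The stated 20 therefore reproduces within one patient. With SD 10.71, the ends of the quoted confidence interval (9.6 and 3.76) need 12 and 66 patients. The plan says that "the sample size requirements would range from 13 subjects for the largest effect in the 95% CI to 67 subjects for the smallest effect", so this also agrees closely. The figures rest on pairing.

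**Step 2: pairing ignored in every trial (a bound, not the plan's rule).** The per-period SD is 10.71/√(2(1 − ρ)). The paired standard error is 10.71/√20 = 2.40. Treating the periods as independent gives about 2.40/√(1 − ρ). At ρ = 0.5 that is 3.39, a ratio of 1.41, and power falls to 61%.

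**Step 3: the plan's rule, with BIC as the index.** Week-3 score only, 20 pairs, no baseline covariates, 100,000 simulated trials per setting. Let S and D be the sample variances of (a + b)/√2 and (a − b)/√2, where a and b are a patient's two week-3 scores, and let P = (S + D)/2. The REML likelihood ratio for the subject effect is 19 × (2 ln P − ln S − ln D) when S > D, and 0 otherwise. The term is dropped when this is below ln 20 = 3.00. A dropped trial is tested on 38 degrees of freedom with independent periods; a retained trial is tested as paired.

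| Assumed ρ | Term dropped | SE in dropped trials vs paired SE, same data | Type I error, rule | Power, rule | Power, always paired | Type I error / power, never paired |
|---|---|---|---|---|---|---|
| 0.2 | 80% | +7% | 4.4% | 83% | 84% | 3.0% / 80% |
| 0.3 | 65% | +11% | 4.2% | 82% | 84% | 2.0% / 76% |
| 0.4 | 46% | +14% | 4.5% | 81% | 84% | 1.3% / 70% |
| 0.5 | 26% | +16% | 4.7% | 82% | 84% | 0.7% / 61% |
| 0.6 | 11% | +18% | 4.9% | 83% | 84% | 0.3% / 48% |

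The third column is the ratio of mean standard errors among dropped trials. It is smaller than 1/√(1 − ρ) because BIC drops the term mainly when the sample correlation happens to be low.

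**Step 4: sensitivity of the drop rate.** With the Akaike criterion the term is dropped in 34% of trials at ρ = 0.4, and power is 83%. A seven-visit simulation with 20 completers drops it less often under BIC: 24–39% at ρ = 0.3, 1–19% at 0.4 depending on how the SD grows over visits, and 2% at 0.5. Its power loss at 0.3 is about 1 point (87.1% against 88.3%). The drop rate thus depends strongly on assumptions. The direction and the small average loss do not.

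**Step 5: does keeping a bounded variance suffice?** Not fully. If the intercept variance is constrained to be non-negative and is estimated at zero, the fit is the same as with the term removed. This happens in about 9% of trials at ρ = 0.3 and 4% at 0.4.

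**The case against.** The strongest reply is that the intercept need not be the only link. The nesting sentence could describe one matrix per participant that spans both periods, and that would keep the pairing with no intercept. This stands as a possible reading. The text does not say it, and testing a separate subject intercept fits better with blocks by period. A reader might infer that dropping the intercept certainly makes the periods independent; the documents support only that it may.

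Second, both baseline covariates are always in the model and absorb part of the between-patient variance, so the relevant ρ is what remains after baseline. That also stands. The week-3 check leaves them out, which is one reason to show a range of ρ. They reduce the residual correlation but do not model it.

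Third, the rule partly protects itself, because the term goes mainly when it matters least. That is correct. A reader might take the last column of the table, or a seven-visit result with the intercept forced out at ρ = 0.4 (standard error about 33% too wide, null rejection 0.9%), as the expected behaviour of the plan. Those figures describe a model that never pairs, which the plan does not prescribe.

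Finally, BIC is itself an assumption here. Section 9.4.2 names it only as an example, and only for the residual matrix.

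**Conclusion.** The point holds in a limited form. Section 9.4.2 leaves the pairing to a data-driven choice and guarantees no other between-period covariance, while Section 9.2 assumes pairing.

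Under the assumptions of the check (week-3 score only, 20 completers, ρ from 0.2 to 0.6, BIC, no baseline covariates, residuals blocked by period), the average cost is 1 to 3 points of power. Power stays above the 80% target and type I error stays slightly below 5%. The practical harm falls on the single trial in which the term is dropped: its primary interval would be about 7–18% wider than the paired model would give.

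Two stronger readings are not supported. One is a false-positive problem: the error is conservative. The other is a biased estimate caused by the withdrawal of sustained period-1 responders (Sections 4.2 and 8.3). With independence forced in every trial and an assumed placebo mean of 25, the estimate was −7.6 to −8.6 for a true −7.5, and unbiased at a true effect of zero. That is not the plan's rule, so it adds a reason to fix the covariance but does not measure the plan's error.

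**What to change.** In Section 9.4.2, delete the test-and-retain clause for the random intercept. State instead that the primary model, and the continuous secondary models that follow it, always include a between-period link within patient. This can be a subject random intercept whose variance is not bounded at zero, or an explicit between-period covariance such as compound symmetry across periods. State that fit indices may choose only the within-period structure.

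In Section 9.4.3, state that the binary response and remission models include the subject effect, and name the fallback if they do not converge, for example generalised estimating equations clustered on patient. A fallback is needed because a logistic model with a subject effect may fail to converge with about 20 patients.

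The cost is a few sentences, with no change to sample size, visits or data collection. The change should be made before the blind is broken.

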## 9.4.3 Analysis of the Secondary Endpoints

Secondary objectives are to evaluate the remission and response rates on the primary outcome measure (MADRS). A similar model to the one described above will be employed, with the difference that the outcome distribution will be specified as binary logistic. Because remission/response is determined based on change from baseline within a period, no baseline covariate will be included in the model. The parameter estimate for the effect of drug on remission/response rate at a given time point will be expressed as an odds ratio with a 95% CI. The remaining secondary analyses of clinical outcomes measured on the interval level (HAMD, BPRS, CADSS, C-SSRS, HAM-A, PANAS, SHAPS, SSI, TEPS, and YMRS) will be conducted in the manner described above for MADRS score. Following the current guidelines of the American Statistical Association (Wasserstein, Schirm et al. 2019), no threshold will be applied to secondary outcomes of this trial. Instead, parameter estimates will be presented alongside both their 95% confidence intervals and the raw p-value.

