#### 2.2 BACKGROUND

# 2.2.1 Ketamine Induces Rapid Antidepressant Effects, but Produces Dissociative Side Effects and has the Potential for Abuse

Mood disorders (MDD and bipolar disorder [BD]) are common, chronic, recurring, serious mental illnesses associated with significant morbidity, and often become life-threatening. A variety of antidepressants have been developed; unfortunately, these medications take weeks to months to achieve their full effects and in the meantime, patients continue to suffer from their symptoms and continue to be at risk of self-harm as well as harm to their personal and professional lives. Although a significant proportion of patients usually respond to currently available medications within three

to four weeks, remission rates are usually low at this point and may take several more weeks to become manifest (Entsuah, Huang et al. 2001). Moreover, up to one-third of patients still do not respond with four consecutive trials of antidepressants. A more rapidly acting antidepressant medication in TRD would significantly impact the treatment of depression and have major health care implications.

In subjects with TRD, ketamine is the only pharmacological treatment that has antidepressant effects that both occur within hours and are sustained for one week or more with a single-administration (Zarate, Singh et al. 2006, Kishimoto, Chawla et al. 2016). In the 2006 study, of 17 subjects, 71% of participants met criteria for antidepressant response (a 50% decrease in HDRS scores), and 29% achieved remission (≤7 HDRS) at 24 hours following infusion of ketamine. Six (35%) subjects maintained response to ketamine for at least one week; in contrast, no subject on placebo responded at Day 1 or Day 7. In a recent study, we found that the antidepressant efficacy of ketamine lasted at least 11 days with single administration in subjects with TRD (Nugent, Ballard et al. 2019). Within six hours to one day, a single ketamine infusion led to response rates comparable to those seen following eight weeks of treatment with monoaminergic based antidepressants. Furthermore, ketamine induced remission in approximately one-third of subjects within one day, which is in stark contrast to that of monoaminergic-based approaches, which usually require 10-14 weeks of chronic daily usage to produce similar remission rates (Trivedi, Rush et al. 2006).

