## 9.1.2 Secondary Endpoints

- Proportion of subjects in remission (defined as MADRS total score  $\leq 10$ ).
  - H0: The 95% confidence interval for the odds ratio (TS-161 versus placebo) predicting MADRS total score ≤10 at 3 weeks will include one.
  - HA: The 95% confidence interval for the odds ratio (TS-161 versus placebo) predicting MADRS total score ≤10 at 3 weeks will be greater than and exclude one.
- Proportion of subjects with response (defined as ≥50% reduction from baseline in MADRS total score).
  - H0: The 95% confidence interval for the odds ratio (TS-161 versus placebo) predicting 50% change from baseline in MADRS total score at 3 weeks will include one.
  - HA: The 95% confidence interval for the odds ratio (TS-161 versus placebo) predicting 50% change from baseline in MADRS total score at 3 weeks will be greater than and exclude one.
- Change from baseline in HDRS, BPRS, CADSS, C-SSRS, HAM-A, MADRS, PANAS, SHAPS, SSI, TEPS, YMRS total scores.
  - H0: The 95% confidence interval for the effect of drug (TS-161 minus placebo) on [all listed outcomes] at the timepoints listed in the Schedule of Events after controlling for baseline scores, will include zero.
  - HA: The 95% confidence interval for the effect of drug (TS-161 minus placebo) on [all listed outcomes] at the timepoints listed in the Schedule of Events after controlling for baseline scores, will be less than and exclude zero.

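### The logistic model for response and remission has no finite odds ratio at any visit where one treatment has no events, and the plan names no fallback

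*Combined protocol and SAP*

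**What the plan says.** Section 9.4.3 defines the binary analysis by reference to the primary one: "A similar model to the one described above will be employed, with the difference that the outcome distribution will be specified as binary logistic". It drops the baseline covariate and then states: "The parameter estimate for the effect of drug on remission/response rate at a given time point will be expressed as an odds ratio". A 95% interval is to accompany it.

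The model carried over from Section 9.4.2 is one "where drug and time are within subjects factors". Its fixed part is: "Fixed effects for drug, time period, and their interaction will be specified". The 3-week effect is taken as a contrast from the drug-by-time interaction, so time here means visit. On correlation, "a subject-specific (random) intercept will be tested and retained if indicated by model fit indices". On estimation, "Maximum likelihood estimation will be implemented, which allows for missingness without excluding the participant; no imputation will be performed".

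Section 9.1.2 states both binary hypotheses at 3 weeks. For remission the wording begins "The 95% confidence interval for the odds ratio (TS-161 versus placebo) predicting MADRS total score", and the test is whether that interval excludes one. The objectives table in Section 3 also hypothesises response at seven visits (230 minutes and Days 1, 2, 3, 7, 14 and 21) and remission at the first six of these.

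Section 9.2 plans 25 recruits and 20 completers, and concedes only that the categorical outcomes have less power. No section mentions sparse cells, penalised or exact estimation, or what to do if the model does not converge.

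**The concern.** A model with drug, visit and their interaction gives each drug-by-visit cell its own log-odds. With seven visits and two treatments that is 14 cells, each holding 20 to 25 subjects. Remission means a MADRS total of 10 or less in patients who enter at 20 or more, and the first rating comes 230 minutes after the first dose. Cells with no events are therefore plausible, above all on placebo and early on. The only placebo response figure in the documents points the same way. In the earlier ketamine study of 17 subjects, Section 2.2.1 reports that "in contrast, no subject on placebo responded at Day 1 or Day 7".

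Reduced power and a missing estimate are different problems, and the plan deals only with the first. Secondary objectives 2 and 3 are judged by this odds ratio and its interval. If the estimate diverges and no rule exists, the replacement method would be chosen after the blind is broken.

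**Working it through.** **1. Cell size.** Section 9.2 gives d = 0.70, two-sided alpha 0.05, 80% power and 20 completers. An exact paired t-test calculation needs 19 (power 82% at 19, 84% at 20). With SD = 7.5/0.70 = 10.7, the ends of the quoted interval (9.6 and 3.76) need 12 and 66, against 13 and 67 stated. The plan's figures are reproduced to within one patient. With 25 recruited, each drug-by-visit cell holds about 20 to 25 subjects. The plan gives no rate or power for response or remission.

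**2. Why an empty cell has no finite estimate.** If a cell has log-odds *a* and no events, each of its subjects contributes 1/(1 + exp(*a* + *b*)) to the likelihood, where *b* is the subject's random intercept. This rises as *a* falls, whatever the other parameters are, so the maximum lies at minus infinity. A numerical check used a random-intercept model with 20 subjects, 14 cells and an empty placebo cell at the first visit:

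| Log-odds fixed in the empty cell | Profile log-likelihood | Log odds ratio at that visit |
|---|---|---|
| -4 | -73.72 | 1.4 |
| -10 | -72.11 | 8.2 |
| -15 | -71.74 | 13.1 |
| -20 | -71.67 | 18.1 |

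The likelihood never turns down, so the optional random intercept does not cure the problem. Visits with events on both treatments keep finite estimates.

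**3. One visit.** P(no placebo event) = (1 - p)^n. The rates p are assumptions.

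| Placebo rate p | n = 20 | n = 25 |
|---|---|---|
| 1% | 82% | 78% |
| 2% | 67% | 60% |
| 5% | 36% | 28% |
| 10% | 12% | 7% |
| 15% | 4% | 2% |
| 20% | 1% | 0.4% |

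**4. Seven visits.** The simulation used correlated binary outcomes (latent normal, within-subject correlation 0, 0.5 or 0.8), n = 20 or 25, and 20,000 runs per setting. It counted placebo cells only. Assumed rates, in visit order:

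- Remission A: 1, 1, 2, 2, 4, 6, 8%. Remission B: 2, 2, 3, 3, 5, 8, 10%.
- Response A: 2, 4, 5, 6, 8, 12, 15%. Response B: 5, 7, 8, 9, 12, 16, 20%.

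| Scenario | At least one empty placebo cell | Day 21 cell empty |
|---|---|---|
| Remission A | 93-100% | 12-19% |
| Remission B | 84-99% | 7-12% |
| Response A | 71-94% | 2-4% |
| Response B | 40-70% | 0.4-1% |
| Flat 15% | 8-24% | 2-4% |
| Flat 20% | 2-8% | 0.3-1% |

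Hand check for Remission A, n = 20, independent visits. The per-visit chances of an empty cell are 0.818, 0.818, 0.668, 0.668, 0.442, 0.290 and 0.189. Then 1 - (0.182² × 0.332² × 0.558 × 0.710 × 0.811) = 0.999, which agrees with the simulation. The expected number of empty cells is 3.89, of which 2.97 (76%) fall at the first four visits, 230 minutes to Day 3.

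**5. What the ketamine figure supports.** If the placebo denominator was 17, zero events give an exact two-sided upper 95% limit of 1 - 0.025^(1/17) = 19.5%. That is compatible with low rates but does not establish them.

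**The case against.** The strongest reply is that the high frequencies belong to visits that 9.1.2 does not test. Its two binary hypotheses sit at 3 weeks, and an empty 230-minute cell does not remove the Day 21 odds ratio. At 3 weeks the assumed rising rates leave the placebo cell empty in only about 0.4-4% of trials for response and 7-19% for remission. This stands, and it limits the point. It does not remove it, because Section 3 also hypothesises effects at the early visits and 9.4.3 promises an odds ratio at a given time point.

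The second reply is that the rates are assumed. The ketamine study used a single infusion, an HDRS criterion and Days 1 and 7. Section 2.2.1 gives no separate placebo denominator. Entry here needs only one failed trial. This also stands: if placebo rates are 15-20% at every visit, empty cells are uncommon.

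Third, no significance threshold applies to secondary outcomes, and a diverging estimate is usually visible in the output. That is fair, but without a threshold the plan relies all the more on the estimate and its interval.

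A reader might infer three stronger things that the documents do not support:

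- *That the analysis will usually fail outright.* Only the affected visits lose their odds ratio.
- *That it fails precisely when the drug works best.* An empty placebo cell depends on the placebo rate, not on the drug effect, and some affected visits would have no events on either treatment.
- *That an exact paired (McNemar) test is the natural cure.* Sections 4.2 and 8.3 withdraw subjects still responding after the extended washout, so they have no second period. A complete-pairs test drops them, whereas the ITT set in 9.3 keeps them.

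**Conclusion.** The concern holds in a limited form. As written, 9.4.3 cannot return a finite odds ratio or usable interval at any visit with no events on one treatment, and it provides no alternative. The mechanism is certain; the frequency rests on assumed placebo rates. Under low, rising rates, some visit is affected in about 84-100% of trials for remission and 40-94% for response, mainly at early visits. At 3 weeks with 20 subjects, the chance is 36% at a 5% placebo rate, 12% at 10% and 4% at 15%, so remission is the endpoint mainly at risk there. The primary MADRS analysis is not touched. This is worth correcting before unblinding, but it does not threaten the trial's main conclusion.

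**What to change.** Amend 9.4.3 before the blind is broken:

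- **Model.** For response and remission, use a penalised logistic model (Firth-type or with a weak prior) with drug, visit, drug-by-visit and period. Handle within-subject correlation by a random intercept or a robust variance, not by fixed subject effects. State the penalty or prior in advance. Every ITT subject stays in, including period-1 responders who do not cross over.
- **Reporting at 3 weeks.** Beside the odds ratio, give the risk difference with a 95% interval, estimated from all ITT subjects.
- **Every visit.** Show counts and percentages by treatment. Where neither treatment has an event, let these be the only summary.
- **Sensitivity.** An exact McNemar comparison at 3 weeks may be added, labelled as restricted to complete pairs.

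The cost is SAP wording and a little programming. The statistical price is that penalised odds ratios are pulled somewhat toward one. In a simulation of 20 pairs with fixed subject and period terms, a true log odds ratio of 1.5 came back at a median of 1.18. The size of the pull depends on the assumed event rates, which is a further reason to avoid fixed subject effects and to report the risk difference as well.
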